3. To evaluate effects of treatment on changes in serum PSA level and changes in PSA doubling time

C. Laboratory and Exploratory Objectives:

1. To determine overall survival
2. To evaluate effects of treatment on number of circulating tumor cells as determined by PSA ELISPOT
3. To evaluate PAP-specific antibody and T-cell immune responses following treatment with sipuleucel-T and DNA vaccine
4. To determine whether PAP-specific immune response is associated with prolonged (1 year) radiographic progression-free survival
5. To determine whether baseline immune responses (Th1 type or regulatory type) predict for immune responses elicited/augmented following treatment with sipuleucel-T +/- DNA vaccine
6. To determine whether treatment elicits immunologic antigen spread to other prostate associated antigens

4. Product Information

A. Sipuleucel-T

PA2024

PA2024 is a recombinant fusion protein consisting of human PAP and GM-CSF. GM-CSF acts as a growth factor and differentiation factor for antigen-presenting cells, including dendritic cells; the purpose of the fusion protein is to direct the PAP antigen to antigen-presenting cells *in vitro*, and promote antigen uptake and processing of the PAP antigen.

Preparation of sipuleucel-T

Patients will undergo a standard 1.5-2.0 blood volume leukapheresis to harvest peripheral blood mononuclear cells. This procedure will be performed either at the UWHC Infusion Center or a contract provider authorized by Dendreon Corporation. Immediately after collection, the product

will be transported by air carrier to a Dendreon-approved national cell processing facility. There, the cell product will be enriched for antigen-presenting cells by proprietary buoyant density centrifugation techniques, and cultured *in vitro* in the presence of PA2024 for 36-44 hours. After the culture period, the cells will be washed and resuspended in Lactated Ringer's Injection, USP. The sipuleucel-T cell product will then be shipped back to the UWHC for infusion at the UWHC Infusion Center. During shipment, sterility testing and cell count data are gathered for final product release for re-infusion. These procedures will all be performed as part of the standard-of-care for the FDA-approved sipuleucel-T product and re-infusion.

B. Plasmid DNA vaccine

pTVG-HP (pTVG4 vector containing cDNA for human PAP)

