High-throughput immunoblot (HTI): A secondary objective of the study will be to determine if patients treated develop “off-target” prostate cancer antigen-specific immune responses as evidence of antigen spread. Exploratory studies will evaluate T-cell responses to non-targeted antigens. However, the primary evaluation will be to evaluate IgG responses to a panel of prostate-associated antigens as we have previously reported in patients treated with vaccines or other immune-modulating agents [54-56]. IgG specific for 126 antigens, including 29 cancer-testis antigens [57, 58] and 97 prostate antigens frequently immunologically recognized [59-62] will be identified by screening a high-density phage array expressing these individual antigens, as we have previously reported [54, 56, 57]. The primary analysis will be conducted using sera obtained at 6 months, and compared with IgG responses identified at baseline, to determine whether IgG specific for individual antigens are elicited over time. Other time points will be assessed to determine the durability and kinetics of immune response development, and confirmatory ELISA studies will be performed if feasible.

REPORTING AND RESPONSE DEFINITION: A positive IgG response will be defined as an immunoreactive spot to a defined antigen, scored by at least 3 of 4 independent reviewers, and detectable to at least 2 of 3 replicates per immunoblot membrane. An IgG response resulting from immunization will be defined as an immunoreactive antigen identified at the 6-month (or other post-treatment time for subsequent analyses) time point that was not identified at the pre-treatment time point.

B. Circulating Tumor Cell (CTC) Enumeration

CTC will be enumerated at the same time points as for immune evaluation (pre-treatment, after 6 weeks, and at quarterly intervals for up to one year) using an ELISPOT methodology as described above, however using capture and detection antibodies specific for PSA [63]. This methodology has been used to count PSA-secreting cells directly from peripheral blood with a frequency < 1 per million PBMC. Given the rarity of these cells, they will not be normally distributed among individual wells of an ELISPOT plate. Hence, PBMC will be plated at

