200,000 cells/well of a 96-well plate, and all spots will be counted (i.e. screening for events among $\sim 20 \times 10^6$ total PBMC). Multiple replicates to determine standard deviation are not feasible. Other methods of CTC enumeration, such as by flow cytometry, may also be used.

C. Serum PSA Doubling Time Response

See Section 12 for further details. Serum PSA doubling-time response will be considered a secondary endpoint. The pre-treatment serum PSA doubling time will be calculated from all serum PSA values available for the three-month period prior to study treatment, not on other treatments for prostate cancer, up to and including the PSA value obtained at screening, using the Memorial Sloan-Kettering Cancer Center nomogram (<http://www.mskcc.org/applications/nomograms/prostate/PsaDoublingTime.aspx>). The post-treatment serum PSA doubling time will be calculated using the same algorithm and using all serum PSA values available during the time patients are on study beginning with the PSA value obtained at day 1.

REPORTING AND RESPONSE DEFINITION: PSA doubling times for the pre-treatment and post-treatment periods will be defined as above. An increase in the PSA doubling time to at least double the baseline value will be defined as a PSA doubling time “response” [64].

11. Reporting Adverse Events

Please see section 14 below, which contains in detail the policy and procedures for patient safety monitoring and adverse event reporting.

A. Definition

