C.2.4. PSA Response

PSA complete response will be defined a decrease in PSA to <0.2 ng/mL. The decrease must be confirmed with PSA measurement a minimum of four weeks later (confirmed PSA CR). PSA partial response will be defined as reduction of at least 50% in baseline PSA.

C.2.5. PSA Doubling Time

PSA doubling time (PSADT) will be defined as the time it takes for the PSA value to double. PSADT will be calculated for each patient pre-treatment and post-treatment. The pre-treatment PSADT will be calculated from all available values obtained within 3-6 months prior to study enrollment, up to and including the baseline value. The post-treatment PSADT will be calculated from all PSA values obtained beginning with the PSA value at day 1 and continuing until the end-of study value. The pre-treatment and post-treatment PSADT will be calculated for each patient as the log 2 divided by the slope of the log PSA line, based on the linear regression model of log (PSA value) on time.

C.2.6. Evaluable for Immune Response

All patients who complete sipuleucel-T treatment at weeks 0, 2, and 4, and who have an immune response assessment at month 6 will be evaluable for immune response.

C.2.7. Analysis Populations

The ITT population consists of all patients who are randomized. The per-protocol population is defined as all patients who have been treated according to protocol, i.e., all inclusion/exclusion criteria are satisfied, and adequate treatment compliance of sipuleucel-T treatment and vaccine (pTVG-HP) is achieved.

D. Study Design

The study is designed as a randomized, two-arm, open-label, single institution pilot trial. Study arms will be defined as follows:

Arm 1: sipuleucel-T – administered intravenously (i.v.) per standard of care biweekly, weeks 0, 2, and 4.

Arm 2: sipuleucel-T – administered intravenously (i.v.) per standard of care biweekly, weeks 0, 2, and 4
 pTVG-HP (100 µg) with rhGM-CSF (208 µg) administered intradermally (i.d.) biweekly 4 times, then every 3 months to complete a 1-year treatment period (i.e. weeks 6, 8, 10, 12, then months 6, 9)

Eligible subjects will be randomly assigned in 1:1 fashion to either Arm 1 or Arm 2.

E. Randomization and Stratification

Eligible patients will be randomized to the two study arms with an allocation ratio of 1:1. The randomization will be based on permuted blocks of size 2-4, stratified by estimated survival (< 18 months, ≥ 18 months) using the Halabi nomogram [50].

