F. Sample Size Estimation and Accrual

The endpoint of this pilot trial will be an immunological endpoint, i.e., the immune response rate at 6 months. Based on published results from a randomized trial using sipuleucel-T only in this population, in which proliferative T-cell responses specific for PAP were detected in 15 of 55 (27.3%) patients after immunization [7], and results from a phase I trial with this DNA vaccine only in which PAP-specific cytolytic T-cell responses were amplified after immunization in 7 out of 12 (58%) evaluable patients [23], it is anticipated that the immune response rate in the sipuleucel-T alone arm (Arm 1) will be 25% and that the addition of the pTVG-HP vaccine (Arm 2) will boost the response rate to at least 75%. An increase of 50% in the immune response rate will be considered as a clinically important difference. The following table shows the required sample sizes (per arm) to detect various differences in the immune response rates between the two arms with 80% power at the one-sided 5% significance level. These calculations are based on the stratified Mantel-Haenszel test with exact p-values.

Table 12.1 *Required sample sizes (per arm) to detect various differences in the immune response rates between the two arms with 80% power at the two-sided 5% significance level*

Immune Response Rate Arm 1 (sipuleucel-T alone arm)	Immune Response Rate: Arm 2 (sipuleucel-T + pTVG-HP vaccine arm)			
	70%	75%	80%	85%
15%	12	10	9	9
20%	15	12	10	9
25%	18	14	12	10
30%	23	18	15	12

A sample size of 14 patients per arm is proposed for this trial. This sample size is sufficient to detect an anticipated difference in the immune response rate of at least 50% (i.e., $\geq 75\%$ in Arm 2 vs. 25% in Arm 1) with adequate power ($\geq 80\%$) at the one-sided 5% significance level. The following table shows the attainable power levels to detect various differences in the immune response rates between arms at the one-sided 5% significance level, assuming a sample size of 28 evaluable (for immune response) patients.

Table 12.2: *Attainable power levels to detect various differences in the immune response rates between the two arms at the one-sided 5% significance level, assuming a sample size of 14 evaluable patients per arm*

	Immune Response Rate: Arm 2 (sipuleucel-T + pTVG-HP vaccine arm)			
Immune Response Rate Arm 1 (sipuleucel-T alone arm)	70%	75%	80%	85%
15%	85%	91%	96%	98%
20%	76%	85%	91%	96%
25%	65%	80%	84%	91%
30%	53%	65%	76%	85%

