A difference in the immune response rate of 55% between the two arms will be detected with at least 84% power. Analogously, a difference in the efficacy response rate of only 40% between the two arms will be detected with 53% power at the one-sided 5% significance level. In order to account for unevaluable patients, 30 eligible patients (15 per arm) will be accrued and randomized. Based on past experience with this patient population treated at our institution, we anticipate that the proposed total number of 30 patients will be accrued within 18 months. Each patient will be followed for at least 12 months.

G. Statistical Analysis Plan

G.1. General

This section outlines the statistical analysis strategy and procedures for the study. If after the study has begun changes are made to primary and/or key secondary objectives, or the statistical methods related to those objectives, then the protocol will be amended.

Summary tabulations will be presented that will display the number of observations, mean, standard deviation, median, range, minimum, and maximum for continuous variables and the number and percent per category for ordinal and categorical data. All endpoints of this study will be presented graphically where possible using boxplots and histograms for continuous variables and (stacked) bar charts for categorical variables. Data analysis will be performed using SAS[®] (SAS Institute Inc., Cary, North Carolina) version 9.2 or greater.

There are many comparisons made between the two trial arms for multiple measurements, both clinical and laboratory. However, since this a pilot study, no adjustment will be made for

multiple comparisons. Except for the primary immunological endpoint, where the comparison between arms will be conducted at the one-sided 0.05 significance level, all other comparisons will be made using a two-sided test at a significance level of 0.05 without adjustment for multiplicity.

G.2. Baseline Comparability

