The number of circulating tumor cells per million PBMC will be summarized in terms of medians and ranges, stratified by study arm and assessment time point. The nonparametric Wilcoxon Signed Rank test will be used to evaluate the effects of treatment on the number of circulating tumor cells within each study arm. The comparison of changes in the number of circulating tumor cells between study arms will be performed using the nonparametric, stratified, Wilcoxon Rank Sum test. Results will be presented graphically over time, and trends (increase, decrease, stable) will be assessed over time.

G.5.2. Analysis for evaluating PAP-specific antibody and T-cell immune responses following treatment with sipuleucel-T and DNA vaccine

PAP-specific antibody and T-cell immune responses, evaluated by multiple different measures described in Section 10.A, following treatment with sipuleucel-T and DNA vaccine will be summarized in tabular format.

G.5.3. Analysis for evaluating whether PAP-specific immune response is associated with prolonged (1 year) progression-free survival

Logistic regression analysis will be conducted to evaluate whether PAP-specific immune response is associated with prolonged (1-year) progression-free survival. The dependent variables will be 12-month progression free survival while treatment arm and PAP-specific immune responses (no vs. yes) will be included as covariates. The results will be reported in terms of odds ratios and the corresponding 95% confidence intervals.

G.5.4. Analysis for evaluating whether baseline immune responses (Th1 type or regulatory type) predict for immune responses elicited/augmented following treatment with sipuleucel-T +/- DNA vaccine

Logistic regression analysis will be conducted to evaluate whether baseline immune responses (Th1-type or regulatory type) predict for immune responses elicited/augmented following treatment with sipuleucel-T +/- DNA vaccine. 6-month and durable immune response at 3,6 or 12 months will be included as dependent variables in this analysis while treatment arm and baseline PAP-specific immune responses (no vs. yes) will be included as covariates. Odds ratios and the corresponding 95% confidence intervals will be reported.

G.5.5. Analysis for evaluating whether treatment elicits immunologic antigen spread to other prostate associated antigens

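### The between-arm CTC test ranks changes and does not adjust for the baseline count: valid, but generally less efficient than a baseline-adjusted rank analysis, by an amount that depends on assumptions

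*Combined protocol and SAP*

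**What the plan says.** The objective is the second laboratory and exploratory one (section 3.C, repeated in 12.B): "To evaluate effects of treatment on number of circulating tumor cells as determined by PSA ELISPOT". For the contrast between arms, section 12.G.5.1 states that the "comparison of changes in the number of circulating tumor cells between study arms will be performed using the nonparametric, stratified, Wilcoxon Rank Sum test". It adds medians and ranges by arm and visit, signed-rank tests within each arm, and graphs over time. It does not name the strata, pick a visit for the between-arm test, or say whether change is absolute or relative. The only stratification factor elsewhere in section 12 is predicted survival (below 18 months versus 18 months or more).

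Baseline CTC is available. Section 10.B says "CTC will be enumerated at the same time points as for immune evaluation", which include a pre-treatment sample, and section 9.B and Appendix B provide 20 mL of blood for it at screening. The assay screens about 20 million cells once per sample, and section 10.B notes that "Multiple replicates to determine standard deviation are not feasible".

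On error rate and size, section 12.G.1 says "all other comparisons will be made using a two-sided test at a significance level of 0.05 without adjustment for multiplicity". Section 12.F says "30 eligible patients (15 per arm) will be accrued and randomized", with 14 evaluable per arm set by the immune-response endpoint. No power, effect size, standard deviation or baseline correlation is given for CTC.

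**The concern.** A change score removes the whole baseline value whether or not that value predicts follow-up. When the baseline is one noisy count, its noise is added to the outcome. Ranks of raw differences have a second weakness with skewed counts: the extreme ranks go mostly to patients who started high. Regressing follow-up on baseline lets the data decide how much baseline to remove, and working with ranks of the counts limits the pull of large values.

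What is at stake is power on an exploratory comparison with at most 15 patients per arm. Section 2.E lists CTC number among the additional clinical endpoints and hopes that the trial will suggest endpoints and biomarkers for later studies, so it is reasonable to use a collected baseline well. No treatment decision or primary conclusion depends on this test.

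**Working it through.** The plan has no CTC power figure to reproduce. The check therefore compares the planned test with a baseline-adjusted one under stated assumptions.

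**Inputs from the documents.** Two arms at 1:1, 15 randomized per arm (14 evaluable), two predicted-survival strata, two-sided 5%, one count per sample from about 20 million cells.

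**Inputs assumed.** Baseline correlation ρ, spread, mean count and effect.

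**1. Large-sample guide, normal data.** With unit variance at each visit, a change score has variance 2(1−ρ) and a baseline-adjusted outcome has 1−ρ². The ratio is (1−ρ²)/[2(1−ρ)] = (1+ρ)/2, which never exceeds 1. At ρ = 0.5 it is 0.75. If the adjusted analysis has 80% power (1.96 + 0.84 = 2.80), the change score has Φ(2.80×√0.75 − 1.96) = Φ(0.46), or 68%. The loss from 80% is 29, 18, 12, 7 and 2 points at ρ = 0, 0.3, 0.5, 0.7 and 0.9.

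**2. Simulated counts, 15 per arm.** Patient-level rates are log-normal (log SD 1) with Poisson counting, two equal strata and a stratum shift of 0.5 on the log scale. The planned test is the stratified rank-sum test on follow-up minus baseline; the alternative is a stratified rank analysis of covariance. With no effect, rejection was 4.1% to 5.6% and 4.2% to 5.7%. Power for a 63% lower count in Arm 2 (ratio e⁻¹ = 0.37), 2,000 trials per cell:

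| Mean-scale, cells per sample | ρ | Raw change | Rank ANCOVA | Gain |
|---|---|---|---|---|
| 5 | 0.3 | 31% | 61% | 30 |
| 5 | 0.5 | 39% | 67% | 28 |
| 5 | 0.7 | 47% | 73% | 26 |
| 5 | 0.9 | 67% | 84% | 17 |
| 1 | 0.3 | 20% | 38% | 18 |
| 1 | 0.5 | 22% | 40% | 18 |
| 1 | 0.7 | 27% | 42% | 15 |
| 1 | 0.9 | 33% | 44% | 11 |

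A repeat of this model put the gains at about 14 to 31 points, so the two runs agree to about 3 points at either end. With 8 per arm the gains fall to about 6 to 16.

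**3. Smaller effects, same model.** For a halving the gain is about 7 to 18 points (for example 16% versus 23% at mean-scale 1, ρ 0.5). For a 30% reduction it is about 0 to 3: 13.2% versus 15.5% (mean-scale 5, ρ 0.7), 20.1% versus 20.2% (5, ρ 0.9), 8.0% versus 9.5% (1, ρ 0.5).

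**4. Separate simulation, 14 per arm, 4,000 trials per cell.** For a halving at ρ = 0.3, 0.5, 0.7 and 0.9, raw change versus rank ANCOVA was:

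- 0.2 per million (4 cells in 20 million): 17/20/25/38% versus 31/34/39/48%, gains of 10 to 14 points.
- 1 per million (20 cells): 19/24/35/63% versus 39/43/55/79%, gains of 16 to 20 points.

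For a 30% reduction at ρ 0.5 the gains were 4.0 and 5.5 points at these two levels. Over all count settings tried with a true effect, the gain ran from about 1 to 42 points. With normal data it ran from 28 points at ρ = 0 to nothing at ρ of 0.8 or more, where the rank ANCOVA was up to about 1 point lower.

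**5. How much is scale and how much is the covariate.** Adding a stratified rank test on log change separates the two:

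| Setting | Raw change | Log change | Rank ANCOVA | Share from scale |
|---|---|---|---|---|
| 5 per sample, 63% lower, ρ 0.7 | 47.8% | 63.8% | 70.3% | 16.0 of 22.5 |
| 5 per sample, 63% lower, ρ 0.9 | 68.7% | 82.7% | 83.8% | 14.0 of 15.1 |
| 1 per million, halved, ρ 0.7 | 35% | 48% | 55% | 13 of 20 |
| 0.05 per million, halved, ρ 0.5 | 13.1% | 13.6% | 20.5% | 0.5 of 7.4 |

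At high correlation most of the gain is scale. In the sparse setting shown, at ρ 0.5, nearly all of it is the covariate.

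**The case against.** The strongest reply is that nothing here is wrong. A stratified rank-sum test on change is valid and conventional for sparse counts. CTC is exploratory, the pilot is sized for another endpoint, and section 12.G.1 openly makes many unadjusted comparisons. All of that stands, and it limits the point to an optional improvement.

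The reply also has force on size. A reader might infer that the plan forfeits a known amount of power, say 11 to 30 points. The documents do not support that: every input behind such a figure is assumed, those values belong to a 63% reduction, and for a 30% reduction the gain nearly vanishes.

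A reader might also put the whole gap down to the missing covariate. The last table shows otherwise at high correlation. G.5.1 leaves open whether change is absolute or relative, and the PSA analysis in 12.G.4.4 uses percentage change. If a relative change were intended, the remaining gain at mean-scale 5 and ρ 0.7 to 0.9 would be about 1 to 7 points (83.8 − 82.7 and 70.3 − 63.8, log change standing in for relative change).

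Finally, a reader might conclude that a true effect would be missed because of this choice. At mean-scale 1 the adjusted test has only 38% to 44% power even for a 63% reduction, so it would usually miss the effect too. At mean-scale 5 and ρ 0.9 the planned test already has 67%.

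What survives is that a collected baseline enters only by full subtraction, and that adjusting for it matched or beat the raw-change test in nearly every count setting tried, at no cost in type I error.

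**Conclusion.** The point holds as a conditional efficiency gain. The planned CTC comparison keeps its 5% level but generally has less power than a rank analysis adjusted for the screening count. Under Poisson-lognormal counts with log SD 1, mean-scale 1 to 5 cells per sample, two equal strata, 15 per arm and ρ from 0.3 to 0.9, the gain is about 14 to 31 points for a 63% lower count, 7 to 18 for a halving and 0 to 3 for a 30% reduction. Other assumptions widen this range in both directions. The direction is well supported. The size cannot be fixed from the documents, and part of it reflects the raw-difference scale. It would be wrong to read this as bias, as an invalid test, or as a threat to the trial's main conclusion.

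**What to change.** In 12.G.5.1, replace the stratified Wilcoxon test on changes with a rank analysis of covariance stratified by predicted survival (below 18 months versus 18 months or more):

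1. At each follow-up visit, rank follow-up CTC and baseline CTC within stratum.
2. Within stratum, regress follow-up rank on baseline rank and keep the residuals.
3. Compare the residuals between arms with the stratified mean-score (Mantel-Haenszel type) test, two-sided 5%.

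Name the strata in the text. Keep the medians, ranges and within-arm signed-rank tests as descriptive, and state whether any change reported there is absolute or relative.

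The cost is a few sentences of SAP text and a few lines in SAS, which section 12.G.1 already specifies. No new samples, patients or visits are needed.

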in patients treated with sipuleucel-T compared to the placebo group (hazard ratio (HR), 0.78. 95% CI: 0.61-0.96, p=0.03) [7]. This survival benefit was also present regardless of prior or subsequent treatment with docetaxel and prednisone. Similar to previous trials, no difference in time to progression was observed (14.6 weeks in the sipuleucel-T group versus 14.4 weeks in the placebo group, p=0.63), contradicting trends observed in the earlier phase studies [7]. With the significant survival benefit detected in the IMPACT phase III trial, FDA approved sipuleucel-T in April 2010 for the treatment of asymptomatic or minimally symptomatic metastatic, castrate-resistant prostate cancer.

C. DNA vaccines can elicit antigen-specific Th1/CTL immune responses

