The detection of antigen spread to other prostate associated antigens, and the identification of specific antigens recognized, will be analyzed descriptively. In addition, logistic regression analysis will be conducted to evaluate whether antigen spread is associated with the generation

of PAP-specific immune responses elicited as a result of treatment. The dependent variables will be the detection of IgG responses to ≥ 1 “off-target” antigen at 6 months (and not present pre-treatment) while treatment arm and 6-month PAP-specific immune responses (no vs. yes) will be included as covariates. The results will be reported in terms of odds ratios and the corresponding 95% confidence intervals.

13. Administrative Considerations

A. Specimen Handling

Upon entry into the study, each subject will be assigned a unique identification number. All materials collected on that subject will be labeled with that number only, for reasons of confidentiality. Lymphocytes collected will be stored in liquid nitrogen, and sera will be aliquoted and stored at -80°C in the research laboratory of the PI for immune analysis.

B. Institutional Review Board

In accordance with federal regulations (21 CFR 312.66), an Institutional Review Board (IRB) that complies with the regulations in 21 CFR 56 must review and approve this protocol and the informed consent form prior to the initiation of the study at each investigator site. In addition, the study cannot be instituted without FDA approval of the vaccine formulations. Finally, the trial will be conducted with adherence to this protocol, following good clinical practice (GCP) guidelines, and in compliance with other applicable regulatory requirements. Any modifications to the protocol must follow the procedure as outlined in Section 16 below.

C. Consent

The local Principal Investigator, co-investigators, or their associates must explain verbally and in writing the nature, duration, and purpose of the study and possible consequences of the treatment. Patients must also be informed that they may withdraw from the study at any time and for any reason without jeopardizing their future treatment. In accordance with Federal regulations (21 CFR 312), all patients must sign the IRB-approved consent form.

14. Data and Safety Monitoring Plan

A. Oversight and Monitoring Plan

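### Ordinary logistic regression in G.5.3 is likely to give an infinite or undefined odds ratio in 28 to 30 patients; G.5.4 and G.5.5 may do so too, and no fallback is named

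*Combined protocol and SAP*

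**What the plan says.** Section 12.G.5.3 reads: "Logistic regression analysis will be conducted to evaluate whether PAP-specific immune response is associated with prolonged (1-year) progression-free survival". The outcome is 12-month progression-free status, and the covariates are treatment arm and immune response (no or yes). G.5.4 models the 6-month and durable immune response on arm and baseline response. G.5.5 models a new IgG response to at least one off-target antigen on arm and 6-month immune response. On reporting, G.5.3 and G.5.5 say: "The results will be reported in terms of odds ratios and the corresponding 95% confidence intervals"; G.5.4 asks for the same quantities.

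The sample is small. Section 12.F gives power "assuming a sample size of 28 evaluable (for immune response) patients" and adds that "30 eligible patients (15 per arm) will be accrued and randomized".

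Elsewhere the plan does provide for small samples or failed assumptions. G.3 uses exact p-values for the primary comparison because the sample is small, and G.4.4 names a nonparametric replacement if the ANOVA of PSA changes is unsuitable. G.5.3 to G.5.5 contain nothing similar.

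**The concern.** A logistic model has no finite maximum-likelihood solution when some combination of the covariates separates those with the outcome from those without it. One simple case is a study arm, or a response group, in which nobody has the outcome. The odds ratio is then zero or infinite, and the usual confidence interval is undefined. Two features make this likely in G.5.3. Few patients are expected to be progression-free at 12 months, and arm and immune response are closely related by design (25% against 75%).

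G.5.3 is the planned test of exploratory objective 4, the link between immune response and 1-year progression-free survival. Section 2.E hopes that the trial will supply immune biomarkers for later studies. If the model fails, the analyst must choose another method after seeing open-label data. Separation is also more likely when the association is real.

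**Working it through.** **Inputs from the documents.** 14 evaluable patients per arm, 15 randomised (12.F); "Eligible patients will be randomized to the two study arms with an allocation ratio of 1:1" (12.E); immune response 25% and 75% (12.F); radiographic progression expected in 50% by 3 months (6.B); median time to progression on sipuleucel-T 11.7 weeks in the first phase III trial and 14.6 weeks in the latest (2.B: "no difference in time to progression was observed (14.6 weeks in the sipuleucel-T group versus 14.4 weeks in the placebo group"); month 3 is week 12 and the 12-month visit is week 48 (study calendar).

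**Assumptions.** Constant hazard; no arm effect on progression beyond that through immune response; true immune-response odds ratio (OR) of 1 or 3.

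**Step 1: the plan's own figure.** Section 12.F gives 14 per arm for "80% power at the one-sided 5% significance level" and says: "These calculations are based on the stratified Mantel-Haenszel test with exact p-values". For 25% against 75%, the pooled normal formula gives 12 per arm, its continuity-corrected form 16 and one-sided Fisher 15. All are within 2 of 14, so N = 28 is taken as given. The documents state no event count or precision for the G.5 models.

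**Step 2: proportion progression-free at 12 months.**
- 50% per 3 months, from registration: 0.5^4 = 6.25%, or 28 × 0.0625 = 1.8 patients. (The 11.7-week median over 48 weeks gives 2^(-48/11.7) = 5.8%, almost the same.)
- 14.6-week median over 48 weeks: 2^(-48/14.6) = 10.2%, or 2.9 patients.
- 50% per 3 months, counted from month 3: 0.5^3 = 12.5%, or 3.5 patients.
- 14.6-week median over the 36 weeks after month 3: 2^(-36/14.6) = 18.1%, or 5.1 patients.

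**Step 3: separation in G.5.3.** The expected arm-by-response cells are 10.5 and 3.5 patients in each arm. All outcomes of the four cells were enumerated, and each pattern was tested by linear programming for an infinite or undefined coefficient (N = 28).

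| Progression-free | Any OR fails, true OR 1 | Any OR fails, true OR 3 | Immune-response OR fails, true OR 1 | Immune-response OR fails, true OR 3 |
|---|---|---|---|---|
| 6.25% | 74% | 80% | 67% | 74% |
| 10.2% | 51% | 61% | 43% | 54% |
| 12.5% | 41% | 51% | 33% | 44% |
| 18.1% | 22% | 32% | 17% | 28% |
| 30% | 7% | 13% | 6% | 12% |
| 50% | 5% | 8% | 5% | 8% |

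With 30 patients, the document-based rows (6.25% to 18.1%) are 2 to 4 points lower.

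Hand check: with no association, the chance that at least one arm has no progression-free patient is 1 - (1 - (1 - p)^14)^2. At p = 0.0625 this is 1 - (1 - 0.405)^2 = 65%; at 0.102, 1 - (1 - 0.222)^2 = 39%; at 0.181, 1 - (1 - 0.061)^2 = 12%. This is only one route to failure, so it lies below the any-OR column, as it should.

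**Step 4: G.5.4 and G.5.5.** The 6-month outcome in G.5.4 has about 14 × 0.25 + 14 × 0.75 = 14 responders in 28, so what matters is how common baseline responses are. That prevalence is not given. For true OR 1 to 3, separation is about 45% to 53% at 10% prevalence, 15% to 24% at 20% and 8% to 15% at 30%. In G.5.5 the outcome rate is not given. Separation is about 53% to 62% if it is 10% or 90%, 18% to 27% if 20% or 80%, and 5% to 13% between 30% and 70%.

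**Step 5: candidate remedies in G.5.3.** Firth regression at 12.5% progression-free and OR 3 gave finite estimates in 1,989 of 2,000 simulated trials (1 rank-deficient, 10 not converged within the iteration limit). Ordinary maximum likelihood fails in about 51% of such trials. The median ratio of upper to lower limit for the immune-response OR was about 330 with Wald limits. Profile-likelihood limits were finite in all of 120 further simulated trials but wider, with a median ratio of about 1,700. Exact conditional regression, conditioned on arm, still gave an infinite limit or a degenerate distribution in about 44% (OR 1) to 60% (OR 4) of trials at 10% progression-free, and in 17% to 34% at 18%.

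**The case against.** The strongest reply has four parts.

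- **The progression rates are extrapolated.** The documents give no 12-month figure. The protocol counts study progression only after month 3, and Section 7.B.2 requires a repeat bone scan for some bone-only progression. Both favour the upper end of the range or beyond. This stands in part. The 18.1% row already uses the month-3 baseline and still gives 22% to 32%. G.4.1 also analyses from randomisation, so the lower rows are relevant. Above 30% progression-free the problem is small.
- **The headline counts failure of either odds ratio, including that for arm.** This is correct. For the immune-response odds ratio alone the document-based range is 17% to 67% at OR 1 and 28% to 74% at OR 3, which is lower but not negligible.
- **A reader might infer that all three models have few events and will often fail.** The documents do not support that. G.5.4 expects about 14 responders in 28 at 6 months, and failure in G.5.4 and G.5.5 depends on rates that are not stated.
- **A reader might also infer that objectives 4, 5 and 6 all rest on these models.** For objective 6 they do not. G.5.5 analyses antigen spread descriptively first and adds the regression to ask about its association with PAP response.

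It is also true that Firth regression adds no information: a limit ratio in the hundreds or more says little about the size of an effect. What it gives is a prespecified result that can be reported and that shows this imprecision.

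**Conclusion.** The point holds for G.5.3 and conditionally for G.5.4 and G.5.5. On the protocol's own progression figures and a constant hazard, G.5.3 would fail to estimate at least one odds ratio in about 22% to 74% of trials with no association and 32% to 80% at a true odds ratio of 3. This rests on design response rates of 25% and 75%, 28 evaluable patients and no separate arm effect on progression. If 30% to 50% of patients were progression-free at 12 months, the figure would be 5% to 13%. For G.5.4 and G.5.5 the risk runs from small to about one half or more, according to rates that the documents leave open.

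The primary comparison is not affected, since G.3 already uses exact methods. The models serve exploratory objectives in a pilot trial, so this is a minor but cheap improvement.

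**What to change.** In G.5.3, and for consistency in G.5.4 and G.5.5, name Firth penalised-likelihood logistic regression with profile-likelihood 95% confidence limits as the single prespecified method. Do not offer exact conditional logistic regression as an alternative: its limits can still be infinite, and a choice between two methods would reopen the decision that the change is meant to settle.

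The cost is one sentence per subsection and a modelling option, with no change to sample size, data collection or patient care. The downsides are slight shrinkage of the odds ratios toward 1 and intervals that remain very wide, which the report should say plainly. In the rare case that arm and immune response coincide completely, no method can separate their effects.
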